16.1 Pharmacokinetics

Population: PK Analysis Set

Non-compartmental computation of PK parameters will be performed using the computer program Phoenix® WinNonlin® version 6.4, or higher (Pharsight Corporation, a Certara Company, Princeton, New Jersey). Phoenix® WinNonlin® or the statistical software SAS® (Statistical Analysis System, SAS-Institute, Cary North Carolina), Windows version 9.2 or higher may be used to produce tables, listings and figures, where appropriate.

Pharmacokinetic parameters will be calculated using standard non-compartmental methods and the actual administered dose and actual sampling times.

For each subject with PK data, PK parameters will be calculated for M4344 and summarized by dose and day according the following groups:

- M4344 alone in Part A
- M4344 alone in Part A2 BID
- M4344 alone in Part A2 QD if applicable
- M4344 in combination after carboplatin in Part B1

The following PK parameters will be evaluated for each of the groups:

C_{max} Maximum observed concentration

C_{max}/Dose The Dose normalized maximum observed concentration. Normalized using the

actual dose, and the formula Cmax/Dose.

Ctrough The concentration observed immediately before next dosing.

AUC_{0-t} Area under the concentration-time curve (AUC) from time zero to the last

sampling time at which the concentration is at or above the lower limit of

quantification.

M4344 First in Human Study

AUC_{0-t}/Dose The Dose normalized AUC_{0-t}. Normalized using the actual dose, and the formula AUC_{0-t}/Dose. Time to reach the maximum observed concentration Cmax tmax Time of last measurable conentration tlast Area under the concentration-time curve (AUC) over a dosing interval. AUC_{0-T} The Dose normalized AUC_{0-T}. AUC_{0-T}/Dose The AUC from time zero (dosing time) extrapolated to infinity, based on the AUC_{0-∞} predicted value for the concentration at t_{last}, as estimated using the linear regression from λz determination. AUC_{0-∞}=AUC_{0-t}+C_{last pred}/λz AUC_{0-∞}/Dose The Dose normalized AUC_{0-∞}. Normalized using actual dose, and the formula $AUC_{0-\infty}/Dose$. **AUC**extra Percentage of AUC_{0-∞} obtained by extrapolation (AUC_{extra}), calculated by $(1 - [AUC_{0-t}/AUC_{0-\infty}]) \times 100.$ Terminal first order elimination rate constant λ-Apparent terminal half-life, $t_{1/2} = \ln 2/\lambda_z$ t1/2 V_z/F Apparent predicted volume of distribution during the terminal phase. $V_z = Dose/(AUC_{0-\infty} * \lambda_z)$ Accumulation ratio for C_{max}, calculated as C_{max D8}/C_{max D1}. (Parts A and A2) Racc(Cmax) Accumulation ratio for AUC_{0-∞}, calculated as AUC_{0-∞} D₈/AUC_{0-∞} D₁. (Part A) R_{acc(AUC0-∞)} Accumulation ratio for AUC_{0-t}, calculated as AUC_{0-tD8}/AUC_{0-tD1} (Part A) Racc(AUC0-t) Accumulation ratio for AUC_{0-T}, calculated as AUC_{0-TD8}/AUC_{0-TD1}. (Part A2) R_{acc(AUC0-T)} Accumulation ratio for AUC, calculated as AUC_{0-τD8}/AUC_{0-∞D1}. (Part A2) Racc(AUC) CL/F The apparent total body clearance. $CL/F = Dose/AUC_{0-\infty}$. CLss/F The apparent total body clearance at steady state. $CLss/f = Dose/AUC_{0-\tau}$. (Part A2) The cumulative amount excreted from time zero (= dosing time) to the end of the Ae₀₋₂₄ current collection interval after dosing. Amount Recovered = Σ (Concentration * Volume). The cumulative percentage of dose excreted from time zero (= dosing time) to the Ae₀₋₂₄% end of the current collection interval after dosing. Percent Recovered = 100*Amount Recovered/Dose.

CLR

The renal clearance of drug: $CL_R = Ae_{0.24}/AUC_{0.24}$.

Additional parameters may be calculated in order to further characterize the PK of M4344 and/or its metabolites.

The following PK parameters will be calculated for diagnostic purposes and listed, but will not be summarized:

- The time interval (h) of the log-linear regression to determine λ_z
- Number of data points included in the log-linear regression analysis to determine λ_z
- Goodness of fit statistic (Rsq) for calculation of λ_z

The calculation of the AUC will be performed using the mixed log-linear trapezoidal method. The actual time of blood sampling (14 significant digits or the SAS format Best12) will be used for PK parameter calculation. In cases where the actual sampling time is missing, calculations will be performed using the scheduled time. For AUC₀₋₂₄, if the actual sampling time at time 24 hours is not equal to the scheduled observation time, AUC₀₋₂₄ will be calculated based on estimated concentration at the scheduled time and not the concentration at the actual observation time. Otherwise, there will be no further imputation of missing data.

Predose samples will be considered as if they had been taken simultaneously with the administration, and will be assigned a time of 0 hours. The same applies to the relevant pre-dose sample (i.e. trough sample) for assessment of multiple dose pharmacokinetics. Concentrations below the lower limit of quantification (LLOQ), will be taken as zero.

The regression analysis should contain data from at least 3 different time points in the terminal phase consistent with the assessment of a straight line on the log-transformed scale. Phoenix WinNonlin best fit methodology will be used as standard. The last quantifiable concentration should always be included in the regression analysis, while the concentration at t_{max} and any concentrations <LLOQ which occur after the last quantifiable data point should not be used.

AUC_{extra} should be less than 20%, the coefficient of correlation (R²) should be \geq 0.8000 and the observation period over which the regression line is estimated should be at least twofold the resulting $t_{1/2}$ itself. If these criteria are not met, then the rate constants and all derived parameters (e.g. λz , $t_{1/2}$, AUC_{0- ∞} AUC_{extra}, Vz/F, CL/F, CL/ss/F) will be included in the parameter outputs and descriptive statistics but will be flagged and discussed appropriately. Any flags will be included in the study specific SDTM.

The following Listings, Tables and Figures will be provided:

Tables/Listings

 Individual plasma M4344 and metabolite concentrations and summary statistics by analyte, group, dose group, and day

[figure not shown]
- Individual cumulative urine M4344 and metabolite amounts and summary statistics by analyte, group and dose group
- Individual urine M4344 and metabolite amounts and summary statistics by analyte, sampling interval, group and dose group
- Individual plasma M4344 and metabolite through concentrations and summary statistics by analyte, group, dose group, and day
- Individual plasma and urine M4344 and metabolite Pharmacokinetic parameters and summary statistics by Group, dose group, and day
- Individual diagnostic M4344 and metabolite PK parameters
- Individual Plasma M4344 and metabolite Concentrations, actual Date/Time of sample collection, scheduled time, time deviation (by Group, dose group, and day)
- Individual urine M4344 and metabolite Concentrations, actual Date/Time of start and end
 of sample collection, scheduled time, urine volume (by Group, dose group, and day)
- The Phoenix WinNonlin NCA Core Output will be provided in a separate listing.

Figures

- Individual M4344 and metabolite concentration-time profiles; linear and Semi-Log Scale (overlaid by Day)
- Individual M4344 and metabolite concentration-time profiles by Group, dose group, and day, linear and Semi-Log Scale
- Median M4344 and metabolite concentration-time profiles by Group, dose group, and day, linear and Semi-Log Scale (n>= 3)
- Median M4344 and metabolite concentration-time profiles; linear and Semi-Log Scale (overlaid by day) (n>= 3) by group and dose group
- Boxplots for M4344 and metabolite PK parameters (e.g. AUC_{0-∞}/Dose, AUC_{0-t}/Dose, C_{max}/Dose)-vs dose by Group and day
- Boxplots for M4344 and metabolite PK parameters (e.g. AUC_{0-∞}/Dose, AUC_{0-t}/Dose, C_{max}/Dose)-vs day by group.
- Scatterplots for M4344 and metabolite PK parameters (e.g. AUC_{0-∞}/Dose, AUC_{0-t}/Dose, C_{max}/Dose)-versus dose by day and Group, (overlaid with medians)
- Observed Log Racc(C_{max}, AUC_{0-t}, AUC_{0-∞}) vs dose for Part A. with reference line at Racc=1

17 References

 Clopper, C. J., & Pearson, E. S. (1934). The Use of Confidence or Fiducial Limits Illustrated in the Case of the Binomial. Biometrika, 26, 404–413.

18 Appendices

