12.3 Concurrent Procedures

All concurrent procedures, which were undertaken any time during the trial, will be summarized according to the eCRF page "Non-Pharmacological Treatment or Procedures" (Parts A and B1) or "Concomitant Procedures" (Part A2).

Concurrent procedures will be derived in the same way as concomitant medications. In case the date values will not allow unequivocal allocation of a procedure as a concurrent procedure, the procedure will be considered a concurrent procedure.

All concurrent procedure data will be listed, including flags for procedures that took place prior to, on or after the date of first dose of a trial drug (M4344 or carboplatin, as applicable), or within 30 days after the last dose of a trial drug (M4344 or carboplatin, whichever was taken last).

13 Treatment Compliance and Exposure

Analysis set: SAF

Dosing information is collected from the "Study Drug Administration: VX-803 – Clinic Dose" (Parts A and B1), "Study Drug Administration Home Dose: VX-803" (Parts A and B1), "Study Drug Administration: Carboplatin" (part B1 only), "End of Dosing" (Parts A and B1), "M4344 Time of Administration" (Parts A2), and "M4344 Administration Details" (Part A2) eCRF pages.

- Part A: M4344 is taken twice a week (on treatment days 1, 4, 8, 11, 15, and 18) of a 21-day treatment cycle.
- Part A2: M4344 is taken twice a day every day of a 21-day treatment cycle. Once daily dosing and additional cohorts with a planned drug holiday may also be explored.
- Part B1:
 - Carboplatin is administered by infusion on treatment day 1 of a 21-day treatment cycle
 - M4344 is taken on treatment days 2 and 9 of a 21-day treatment cycle. An additional cohort with one additional dose on day 5 may be explored.

Total number of administrations of M4344

Total number of administrations is calculated as the sum of administrations that a subject received across cycles where actual dose received is > 0 mg or the eCRF field for "Did the subject take the dose of VX-803?" on the "Study Drug Administration Home Dose: VX-803" is marked as "Yes" or if the eCRF field for "Was VX-803 administered?" on the "Study Drug Administration: VX-803 – Clinic Dose" is marked as "Yes."

Total number of infusions of carboplatin (part B1 only)

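### CL/F and Vz/F are defined on AUC0-∞ without a first-dose limit, so Part A Day 8 values include carry-over and can look like a fall in clearance

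*SAP*

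**What the plan says.** All references are to the integrated analysis plan for Parts A, A2 and B1. The Part C plan only lists concentrations and is not affected.

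- Section 16.1 states that "PK parameters will be calculated for M4344 and summarized by dose and day according the following groups". The groups are Part A, Part A2 BID, Part A2 QD if applicable, and Part B1. The listed parameters are to be evaluated for each group, and the table list in the same section again asks for summaries by group, dose group and day.
- The entry "CL/F The apparent total body clearance" is dose divided by AUC0-∞. Vz/F is dose divided by AUC0-∞ times λz. Neither entry names a day or a part.
- Other entries are restricted. CLss/F, described as "The apparent total body clearance at steady state", is dose over AUC0-τ and labelled Part A2. Racc(AUC0-∞) is the ratio "calculated as AUC_{0-∞} D₈/AUC_{0-∞} D₁. (Part A").
- On pre-dose samples, which are assigned time 0, the section adds: "The same applies to the relevant pre-dose sample (i.e. trough sample) for assessment of multiple dose pharmacokinetics". It describes no subtraction of residual drug.
- If AUCextra is not below 20%, or the regression criteria are not met, the derived parameters stay in the outputs and descriptive statistics and are flagged.

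**The concern.** Dose over AUC0-∞ estimates apparent clearance when the AUC comes from that dose alone. After repeated dosing, the area from the current dose to infinity also contains what is left of earlier doses. One dose divided by that larger area gives too small a clearance, and Vz/F shrinks with it.

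The Part A accumulation ratio shows that AUC0-∞ is computed on Day 8 there. With no day limit on CL/F and Vz/F, a programmer following Section 16.1 would produce Day 8 values. In Part A no steady-state clearance stands beside them, and Vz/F has no multiple-dose counterpart in any part. PK is a stated objective of all three parts (Section 5). A drop from Day 1 to Day 8 could be read as time-dependent clearance when it is only accumulation.

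**Working it through.** The plan gives no figure to reproduce. The check has four steps.

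**1. Identity for Part A.** For equal doses:

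CL/F(Day 8) = Dose / AUC0-∞(Day 8) = [Dose / AUC0-∞(Day 1)] × [AUC0-∞(Day 1) / AUC0-∞(Day 8)] = CL/F(Day 1) / Racc(AUC0-∞).

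This is arithmetic and needs no PK model. The same holds for Vz/F if λz is unchanged.

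**2. Size of the understatement.** The plan states no half-life, so a range is assumed. With linear, time-invariant, one-compartment kinetics, R = 1 + Σ 2^(−tᵢ / t½) over the earlier doses, and the understatement is 1 − 1/R. The lags tᵢ come from the schedules in Section 13:

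- Part A: M4344 is taken twice a week ("on treatment days 1, 4, 8, 11, 15, and 18) of a 21-day treatment cycle"), so Day 8 follows doses 96 h and 168 h earlier.
- Part A2 BID: 14 earlier doses, at 12-h steps up to 168 h. Part A2 QD: 7 earlier doses, at 24-h steps.
- Part B1: doses on Days 2 and 9, so one earlier dose, 168 h before Day 9.

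Worked example, Part A at 24 h: R = 1 + 2^(−4) + 2^(−7) = 1 + 0.0625 + 0.0078 = 1.070, and 1 − 1/1.070 = 6.6%.

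| Assumed t½ | Part A Day 8 | A2 BID Day 8 | A2 QD Day 8 | B1 Day 9 |
|---|---|---|---|---|
| 6 h | 0.0% | 25.0% | 6.2% | 0.0% |
| 12 h | 0.4% | 50.0% | 25.0% | 0.0% |
| 24 h | 6.6% | 70.5% | 49.8% | 0.8% |
| 48 h | 25.3% | 82.8% | 68.8% | 8.1% |

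The A2 columns apply only if Day 8 CL/F is computed from AUC0-∞ there. If the optional Day 5 dose in Part B1 is explored, the lags before Day 9 are 96 h and 168 h, and the Part A figures apply.

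A numerical oral one-compartment model (true CL/F 10, absorption rate 1/h, t½ 12 h) gives Day 8 values of 9.96 (Part A), 4.85 (BID) and 7.39 (QD), in line with the table.

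**3. Effect of the acceptance criteria.** If sampling stops at time T after the dose, AUCextra is about 2^(−T/t½). Requiring less than 20% means t½ < T × ln 2 / ln 5. Sampling windows are an assumption.

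- A2, sampled over one interval: t½ is below 5.2 h (BID) or 10.3 h (QD). R is then at most 1.25, and the understatement at most 1 − 1/1.25 = 20%.
- Part A, 24-h sampling: t½ is below 10.3 h and the understatement at most about 0.2%.
- Part A, 72-h sampling (Day 8 to Day 11): t½ is below 31.0 h, R is at most 1.140, and the understatement at most about 12%.

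**4. Behaviour of the fix.** In the oral model, the first-dose CL/F is 10.00 in every case. On Part A2 Day 8, dose over AUC0-τ gives 10.00 at 12 h, 10.04 to 10.06 at 24 h, and 10.68 to 10.82 at 48 h, where steady state is not yet reached. The same formula on Part A Day 8 with a 72-h interval gives 10.13, 10.70 and 11.58 at 12, 24 and 48 h, so it is not a clean substitute there.

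**The case against.** The best reply concerns Part A2. The only Day 8 use of AUC0-∞ in the plan is the Part A accumulation ratio. For A2 both AUC ratios put AUC0-τ on Day 8, one of them over Day 1 AUC0-∞, and CLss/F is supplied. Together with the reference to standard non-compartmental methods, the natural reading is CL/F after the first dose and CLss/F at steady state. This stands as far as it goes: a biased Day 8 CL/F in A2 is left open by the wording but not prescribed. It does not cover Vz/F, which has no steady-state form, and it does not help Part A.

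Second, every table entry of 25% or more would fail the plan's own criteria if sampling stays within one dosing interval. For example, Part A at 48 h needs a regression window of 96 h, but the next dose comes after 72 h. This also stands, with two limits: failing values are kept in the descriptive statistics, and the flag signals extrapolation, not carry-over.

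Third, Part A also tabulates Racc(AUC0-∞) and plots it against dose with a reference line at 1, so accumulation is visible. That helps a careful reader. It also shows that Day 8 CL/F adds nothing to Day 1 CL/F and Racc at equal doses.

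Finally, these outputs are descriptive, and Section 15.1 defines the MTD by DLT counts. That stands and keeps the severity low.

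**Conclusion.** The point holds as a minor one. Followed as written, Section 16.1 yields a Part A Day 8 CL/F equal to Day 1 CL/F divided by Racc(AUC0-∞), given equal doses, and Vz/F likewise if λz is unchanged. These values do not estimate clearance or volume. The size depends on a half-life that the plan does not give: negligible in Part A at 12 h or less, about 7% at 24 h and 25% at 48 h. In Part B1 with doses on Days 2 and 9 it is small.

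A reader might infer that all parts are understated by their accumulation ratio, and that Part A2 would lose half or more of its clearance. The documents do not support this. The identity is exact only for Part A's ratio. In A2, Racc(AUC) is about 1 under linear kinetics near steady state, and Racc(AUC0-τ) matches only approximately (2.13 against 2.06 for BID at 12 h). Part B1 has no Day 8 dose and no accumulation ratio. The large A2 figures need both an unstated Day 8 AUC0-∞ and half-lives that would fail the acceptance criteria under one-interval sampling. If clearance really changes by Day 8, the ratio mixes that change with carry-over.

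**What to change.** In Section 16.1:

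- State that CL/F and Vz/F based on AUC0-∞ are reported for the first M4344 dose only: Day 1 in Parts A and A2, Day 2 in Part B1.
- For Part A2 Day 8, use the plan's CLss/F and add a matching Vz/F = Dose / (AUC0-τ × λz), noting that both assume steady state.
- For Part A Day 8, drop the clearance and volume based on AUC0-∞, or keep them with a footnote that they include carry-over from earlier doses. Do not extend CLss/F to Part A.

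The cost is a few lines of wording. Part A then has no Day 8 estimate of apparent total clearance, but the entry it loses did not estimate clearance. Accumulation in Part A remains reported through Racc.

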Appendix I Safety Laboratory Test Panels

Serum Chemistry ^a	Hematology ^a	Urinalysis ^{a,0}
Glucose Blood urea nitrogen/Urea® Creatinine Sodium Potassium Calcium Chloride Magnesium Bicarbonate Inorganic phosphate Total bilirubin Direct bilirubin Creatine kinase¢ Alkaline phosphatase Aspartate aminotransferase Lactate dehydrogenase Uric acid [©] Thyroid stimulating hormone¢	Hemoglobin Erythrocytes Mean corpuscular hemoglobin Mean corpuscular hemoglobin concentration Mean corpuscular volume Platelets Leukocytes Differential (absolute and/or percent ^e): Eosinophils Basophils Neutrophils Lymphocytes Monocytes Coagulation studies* Activated partial thromboplastin time Prothrombin time Prothrombin time Prothrombin time International Normalized Ratio	Leukocyte esterase Nitrite Urobilinogen Urine protein pH Urine blood Specific gravity Urine ketone Urine bilirubin Urine glucose

- a. Labs will be performed at Screening (Protocol Table 1) and at specified times during the Treatment and Follow-up Period (Protocol Tables 2, 3, 4, and 5)
- b. If blood urea nitrogen cannot be collected, urea may be substituted.
- c. Creatine kinase, uric acid, thyroid stimulating hormone, and coagulation parameters will only be tested at Screening.
- d. If urinalysis results are positive for leukocyte esterase, nitrite, protein, or blood, microscopic examination of urine will be performed and results provided for leukocytes, erythrocytes, crystals, bacteria and casts.
- e. Per local laboratory availability.

ELECTRONIC SIGNATURES

Document: ctp-ms201922-0001-iap-main-text-body-v1

Signed By	Event Name	Meaning of Signature	Server Date (dd-MMM-yyyy HH:mm 'GMT'Z)
PPD	Task Completed (Approval eSign): Approved	Business Approval	01/17/2019 12:40:06
PPD	Task Completed (Approval eSign): Approved	Business Approval	01/21/2019 10:51:03

M4344 in Solid Tumors IAP Version 1.0

Integrated Analysis Plan

Clinical Study Protocol Identification No. MS201922-0001

Title

An Open-Label Study of the Safety, Tolerability, and Pharmacokinetic/Pharmacodynamic Profile of M4344 (formerly VX-803) as a Single Agent and in Combination with Cytotoxic Chemotherapy in Participants with Advanced Solid Tumors

Study Phase I

Investigational Medicinal

Product(s)

M4344

Clinical Study Protocol

Version

29 January 2020 / Version 8.0

Integrated Analysis Plan

Author

Coordinat	ing Author	
PPD	, Merck	PPD
Function		Author(s) / Data Analyst(s)
PPD		PPD

SAE Serious Adverse Event SAF Safety Analysis Set

SD Stable Disease or Standard Deviation

SDTM Study Data Tabulation Model

SOC System Organ Class

TEAE Treatment-Emergent Adverse Event

WHO-DD World Health Organization Drug Dictionary

3 Modification History

Unique Identifier for Version	Date of IAP Version	Author	Changes from the Previous Version
1.0	14Apr2021	PPD	N/A: First version

4 Purpose of the Integrated Analysis Plan

The purpose of this IAP is to document technical and detailed specifications for the analysis of data collected for protocol MS201922-0001 - Part C.

The study was prematurely terminated by the sponsor and an abbreviated study report will be written.

Results after the database lock for the final analysis will be included in the abbreviated Clinical Study Report (aCSR). Additionally, the planned analyses identified in this IAP may be included in regulatory submissions or future manuscripts. Any post-hoc, or unplanned analyses performed to provide results for inclusion in the aCSR but not identified in this prospective IAP will be clearly identified in the aCSR.

The IAP is based on Section 8 (Statistics) of the study protocol and protocol amendments and is prepared in compliance with ICH E9. It describes analyses planned in the protocol and protocol amendments.

5 Objectives and Endpoints

Objectives	Endpoints (Outcome Measures)	IAP section
Primary		
To evaluate the efficacy of M4344 in terms of confirmed objective response.	Objective response according to Response Evaluation Criteria in Solid Tumors version 1.1 (RECIST v1.1) as assessed by Investigator	Section 14.1
To evaluate the safety and tolerability of M4344	Occurrence of: treatment-emergent adverse events (TEAEs) and treatment-related TEAEs, as per NCI-CTCAE v5.0 Laboratory abnormalities Clinically significant abnormal vital signs Clinically significant abnormal ECGs	Section 15
Secondary		
To evaluate the duration of response for subjects receiving M4344	Duration of response according to RECIST v1.1, as assessed by Investigator	Section 13
To evaluate the overall survival (OS) for subjects receiving M4344	os	Section 14.3
To evaluate the progression-free survival (PFS) for subjects receiving M4344	PFS according to RECIST v1.1 as assessed by Investigator	Section 14.4
To evaluate the PK of M4344	No PK parameter estimates of M4344 will be provided.	Section 16.1

6 Overview of Planned Analyses

Study Part C was to explore potential antitumor efficacy and aimed to confirm the safety and tolerability of single agent M4344. Parts C1-C3 planned to enroll participants whose tumors harbored loss-of-function mutations in one or more of the following genes ARID1A (C1), ATRX and/or DAXX (C2), ATM (C3).

The study Part C was stopped after 13 subjects were enrolled; and therefore, only a final analysis will be conducted. Due to the low number of cohorts and participants, it was decided to reduce the scope of the TLFs. Data will not be summarized per Part. Where appropriate, only listings will be provided. Details are provided in the respective sections.

Statistical analyses will be performed using CDISC SDTM data. These SDTM data contain as clean as possible eCRF data, as well as external data, including laboratory data, biomarker data, and electrocardiogram data. A data review meeting will be held prior to the database lock. In addition, no database can be locked until this IAP has been approved.

